5.3. Lifestyle Considerations

The following guidelines are provided:

5.3.1. Meals and Dietary Restrictions

- Participants must abstain from all food and drink (except water) at least 4 hours prior to any safety laboratory evaluations.
- While participants are confined, their total daily nutritional composition should be approximately 55% carbohydrate, 30% fat, and 15% protein. The daily caloric intake per participant should not exceed approximately 3200 kcal.

5.3.2. Caffeine, Alcohol, and Tobacco

- Participants will abstain from caffeine-containing products for 24 hours prior to the start of dosing in the CRU and during clinical confinement at the CRU.
- Participants will abstain from alcohol for 24 hours prior to admission to the CRU and continue abstaining from alcohol during clinical confinement at the CRU. Participants may undergo an alcohol breath test or blood alcohol test at the discretion of the investigator.
- Participants will abstain from the use of tobacco- or nicotine-containing products for 24 hours prior to dosing and during clinical confinement at the CRU.

5.3.3. Activity

- Participants will abstain from strenuous exercise (eg, heavy lifting, weight training, calisthenics, aerobics) for at least 48 hours prior to each blood collection for clinical laboratory tests. Walking at a normal pace will be permitted.

5.3.4. Contraception

The investigator or his or her designee, in consultation with the participant, will confirm that the participant has selected an appropriate method of contraception for the individual participant and his or her partner(s) from the permitted list of contraception methods (see [Appendix 4 Section 10.4.4](#)) and will confirm that the participant has been instructed in its consistent and correct use. At time points indicated in the [SoA](#), the investigator or designee will inform the participant of the need to use acceptable effective contraception consistently and correctly and document the conversation and the participant's affirmation in the participant's chart (participants need to affirm their consistent and correct use of at least 1 of the selected methods of contraception) considering that their risk for pregnancy may have changed since the last visit. In addition, the investigator or designee will instruct the participant to call immediately if the selected contraception method is discontinued or if pregnancy is known or suspected in the participant or partner.

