4.2.1. Choice of Contraception/Barrier Requirements

Human reproductive safety data are not available for PF-06823859, but there is no suspicion of human teratogenicity based on the intended pharmacology of the compound. Therefore, the use of a highly effective method of contraception is required (see Appendix 4).

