10.4.2. Female Participant Reproductive Inclusion Criteria

A female participant is eligible to participate if she is not pregnant or breastfeeding, and at least 1 of the following conditions applies:

- Is not a WOCBP (see definitions below in [Section 10.4.3](#)).

OR

- Is a WOCBP and using a contraceptive method that is highly effective (with a failure rate of <1% per year), preferably with low user dependency, as described below during the intervention period and for at least 150 calendar days after the last dose of study intervention, which corresponds to the time needed to eliminate any reproductive safety risk of the study intervention(s). The investigator should evaluate the effectiveness of the contraceptive method in relationship to the first dose of study intervention.
- Is a WOCBP and using a contraceptive method that is highly effective (with a failure rate of <1% per year), with high user dependency, as described below during the intervention period and for at least 150 calendar days after the last dose of study intervention, which corresponds to the time needed to eliminate any reproductive safety risk of the study intervention(s). In addition, a second effective method of

contraception, as described below, must be used. The investigator should evaluate the effectiveness of the contraceptive method in relationship to the first dose of study intervention.

The investigator is responsible for review of medical history, menstrual history, and recent sexual activity to decrease the risk for inclusion of a woman with an early undetected pregnancy.

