10.4.4. Contraception Methods

Contraceptive use by men or women should be consistent with local availability/regulations regarding the use of contraceptive methods for those participating in clinical trials.

Highly Effective Methods That Have Low User Dependency

1. Implantable progestogen-only hormone contraception associated with inhibition of ovulation.*
2. Intrauterine device.
3. Intrauterine hormone-releasing system.
4. Bilateral tubal occlusion (eg, bilateral tubal ligation).
5. Vasectomized partner.
 - A vasectomized partner is a highly effective contraceptive method provided that the partner is the sole sexual partner of the WOCBP and the absence of sperm has been confirmed. If not, an additional highly effective method of contraception should be used. The spermatogenesis cycle is approximately 90 days.

Highly Effective Methods That Are User Dependent

6. Combined (estrogen- and progestogen-containing) hormonal contraception associated with inhibition of ovulation.
 - Oral;
 - Intravaginal;*
 - Transdermal;*
 - Injectable.*
7. Progestogen-only hormone contraception associated with inhibition of ovulation.
 - Oral;*
 - Injectable.*
8. Sexual abstinence.

- Sexual abstinence is considered a highly effective method only if defined as refraining from heterosexual intercourse during the entire period of risk associated with the study intervention. The reliability of sexual abstinence needs to be evaluated in relation to the duration of the study and the preferred and usual lifestyle of the participant.

One of the following effective barrier methods must be used in addition to the highly effective methods listed above that are user dependent:

- Male or female* condom with* or without spermicide;
- Cervical cap*, diaphragm*, or sponge with spermicide*;
- A combination of male condom with either cervical cap*, diaphragm*, or sponge with spermicide* (double-barrier methods).

*) Not approved in Japan

CCI

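### For women of childbearing potential on user-dependent contraception, the visit check in Protocol 5.3.4 is met by one method, while Appendix 4 requires two

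*Protocol*

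**What the plan says.** Protocol 5.3.4 has two steps. When the method is chosen, the investigator or designee "will confirm that the participant has selected an appropriate method of contraception" from the list in 10.4.4. Then, at the time points in the Schedule of Activities (SoA), the site reminds the participant about contraception and charts the conversation and the participant's affirmation. The threshold for that affirmation is that "participants need to affirm their consistent and correct use of at least 1 of the selected methods of contraception". The same section adds that the site "will instruct the participant to call immediately if the selected contraception method is discontinued".

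Appendix 4 sets the underlying requirement. One of the categories that 10.4.2 admits is a participant who "Is a WOCBP and using a contraceptive method that is highly effective (with a failure rate of <1% per year), with high user dependency". For her the text continues: "In addition, a second effective method of" contraception is mandatory. The duration is the intervention period plus at least 150 calendar days after the last dose. Section 10.4.4 repeats the rule: "One of the following effective barrier methods must be used in addition to the highly effective methods listed above that are user dependent".

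The SAP says nothing on contraception.

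**The concern.** The affirmation is the scheduled, documented evidence that the contraception requirement is still being met after dosing. For one group of participants its threshold is lower than the requirement it is meant to verify. A site could follow 5.3.4 exactly and chart a satisfactory check for a participant who has fallen out of line with Appendix 4.

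What is at stake is participant and fetal safety. Section 2.3 names contraception and pregnancy testing as the mitigations that go with enrolling WOCBP before the enhanced pre- and postnatal study has been done. Section 4.2.1 says that human reproductive safety data are lacking. Because this is a single-dose study, the protection depends on what participants do after the dose.

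**Working it through.** No sample size, power or event figure bears on this point, so the check is a comparison of text with a little arithmetic on timing.

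**Step 1. Methods required against methods needed for the affirmation, by category.**

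| Participant category | Appendix 4 requires | 5.3.4 affirmation needs | Conflict |
|---|---|---|---|
| WOCBP, user-dependent highly effective method (10.4.2, 10.4.4) | 2 (that method plus a barrier) | 1 | Yes |
| WOCBP, low-user-dependency method (10.4.2, 10.4.4) | 1 | 1 | No* |
| Male participant using a condom (10.4.1) | 1 (the partner's method is only advised) | 1 | No |

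*Exception: for a vasectomized partner who does not meet the conditions in 10.4.4, an additional highly effective method is called for.

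**Step 2. How likely the affected category is here.** Section 10.4.4 marks the methods not approved in Japan. Among the user-dependent methods, only combined oral contraception and abstinence are unmarked. The only unmarked barrier is the male condom without spermicide. Apart from abstinence, the one pairing without that mark is therefore an oral contraceptive plus a male condom.

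**Step 3. Follow that pairing through a check.**

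| Still in use | Can truthfully affirm under 5.3.4 | Meets 10.4.2 and 10.4.4 | Highly effective method in use |
|---|---|---|---|
| Pill and condom | Yes | Yes | Yes |
| Pill only | Yes | No | Yes |
| Condom only | Yes | No | No |
| Neither | No | No | No |

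The affirmation separates only the last row from the rest. The two middle rows are the gap, and the condom-only row is the more serious of them.

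**Step 4. Timing does not explain the difference.** Day 157 is 157 − 1 = 156 days after the Day 1 dose. With a visit 3 days early it is 156 − 3 = 153 days. Follow-up therefore runs past 150 days. The SoA contraception row does not read cleanly in the text available to me, so I do not list the check days; the conflict does not depend on them.

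**Step 5. Scale of the 150 days.** Section 2.2.2.2 gives a terminal half-life of 22.73 to 29.08 days. 150 / 29.08 = 5.2 and 150 / 22.73 = 6.6, so the period spans about 5 to 7 half-lives.

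**Step 6. Does the rest of 5.3.4 restore the second method?** The selection step and the call-in instruction each speak of one method. The reference to 10.4.4 is attached to the initial selection. The affirmation sentence carries its own threshold.

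**The case against.** The strongest reply is that 5.3.4 does not displace Appendix 4. Inclusion criterion 1 makes Appendix 4 an eligibility requirement, and 5.3.4 ties selection to the 10.4.4 list, which contains the barrier sentence. The affirmation is a charted conversation with no stated pass or fail. The words can also be read as a common floor for a paragraph that covers both sexes and all method types. This stands to the extent that the protocol cannot be said to permit one method for these women. It does not remove the mismatch, because the floor is what the site must document.

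The second reply is that other safeguards exist. A woman who stops the pill is told to call. Section 6.8 requires concomitant treatments to be recorded with start and stop dates and asked about at each clinic visit. Section 8.2.10 adds pregnancy tests at SoA visits, after a missed cycle or on suspicion. These narrow the condom-only case in particular. They do not reach a dropped condom in the same way, and pregnancy tests detect an exposure without preventing it.

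A reader might infer more than the documents support:

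- **That every participant is affected at every check.** Step 1 shows otherwise.
- **That abstinence is a good example.** It sits in the user-dependent list, so the barrier sentence literally applies. But "Sexual abstinence is considered a highly effective method only if defined as refraining from heterosexual intercourse" throughout the period of risk, so a woman who truthfully affirms it leaves no practical gap.
- **That the wording on effectiveness is a second contradiction.** Section 4.2.1 says "the use of a highly effective method of contraception is required", while 5.3.4 uses a looser term. Section 5.3.4 also covers men, whose condom is not on the highly effective list, so a generic term is natural there.
- **That harm is expected.** Section 4.2.1 finds no ground to suspect human teratogenicity from the intended pharmacology, and 2.3 reports no risk to reproductive organs identified in mature monkeys.

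**Conclusion.** The point holds as an internal inconsistency limited to WOCBP using user-dependent methods. For them Appendix 4 requires two methods and the documented affirmation needs one, so a truthful affirmation can coexist with a breach of Appendix 4. The other safeguards reduce the gap without closing it.

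The size in practice is unknown. The protocol plans about 12 participants of both sexes and does not say how many will be WOCBP or which methods they will use. No endpoint or analysis is affected. The change is worth making because it is cheap and bears on participant safety, but it is not a defect that undermines the study.

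The conclusion rests on reading the affirmation sentence literally, as site staff filling in a checklist would. It takes no position on which contraceptive rule is right.

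**What to change.** Reconcile Protocol 5.3.4 with 10.4.2 and 10.4.4 so that the visit-level affirmation and Appendix 4 state the same number of methods for each participant category: male participants, WOCBP on low-user-dependency methods, and WOCBP on user-dependent methods. Which rule applies is for the sponsor to decide. The cost is one sentence in the protocol and one line in the site's visit checklist.

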5.4. Screen Failures

Screen failures are defined as participants who consent to participate in the clinical study but are not subsequently randomly assigned to study intervention/enrolled in the study. Screen failure data are collected and remain as source and are not reported on the CRF.

Individuals who do not meet the criteria for participation in this study (screen failure) may not be rescreened.

6. STUDY INTERVENTION(S) AND CONCOMITANT THERAPY

Study intervention is defined as any investigational intervention(s), marketed product(s), placebo, medical device(s), or study procedure(s) intended to be administered to a study participant according to the study protocol.

For the purposes of this protocol, study intervention refers to PF-06823859 and placebo.

6.1. Study Intervention(s) Administered

PF-06823859 100 mg/mL Solution for Injection will be supplied by Pfizer and packaged in a single-use carton containing a 6 mL glass vial sealed with a stopper and aluminum flip off cap. Each vial contains PF-06823859 in 1.35 mL of solution. Placebo for PF-06823859 100 mg/mL Solution for Injection will also be provided.

These products will be supplied to the CRU as open label packaged supplies and must be received at the site by unblinded site staff. The site will take all necessary precautions to maintain the investigator and site personnel blind.

6.1.1. Administration

Intervention Name	PF-06823859 100 mg/mL	Placebo for PF-06823859
ARM Name (group of patients receiving a specific treatment, or no treatment)	Active	Placebo
Type	Biologic	Biologic
Dose Formulation	Solution for injection	Solution for injection
Unit Dose Strength(s)	100 mg/mL	0 mg/mL
Dosage Level(s)	300 mg, 900 mg	Placebo
Route of Administration	Intravenous	Intravenous
Use	Experimental	Placebo
IMP or NIMP	IMP	IMP
Sourcing	Provided by the sponsor.	Provided by the sponsor.
Packaging and Labeling	Study intervention will be provided in vials packaged in individual cartons. Each vial and carton will be labeled as required per country requirement.	Study intervention will be provided in vials packaged in individual cartons. Each vial and carton will be labeled as required per country requirement.

Participants will receive study intervention at approximately 0800 hours on Day 1 (plus or

minus 4 hours). Study intervention does not require fasting, but it should be noted that the safety laboratory tests at Day -1 prior to the dose of study intervention need a fast of at least 4 hours. Investigator site personnel will administer study intervention as a 60-minute IV using a calibrated infusion pump. Study medication must not be administered as an IV push or bolus. The infusion rate, amount of volume infused, start and stop time of the infusion will be recorded. Time 0 is the time when the study intervention infusion begins. The infusion will be on the opposite arm from PK sampling.

Administer study intervention according to the IP Manual.

6.1.1.1. Intravenous Infusion Discontinuation

- If a participant experiences symptoms typical of an allergic reaction, the study intervention infusion should be discontinued immediately and permanently.
- If a participant experiences symptoms typical of IRR (eg, lightheadedness, nausea, chills, fever), the study intervention infusion should be stopped. At the discretion of the investigator, the infusion can be restarted at a slower rate if symptoms are resolved within 1 hour after the stop of infusion. If symptoms return, then the study intervention infusion should be discontinued immediately and permanently.
- In the event that there is an infusion interruption, the entire duration of study intervention infusion, from the initial start of infusion to the completion of infusion, should not exceed 3 hours. Participants will receive appropriate treatment at the discretion of the investigator.

6.2. Preparation, Handling, Storage, and Accountability

1. The investigator or designee must confirm appropriate temperature conditions have been maintained during transit for all study interventions received and any discrepancies are reported and resolved before use of the study intervention.
2. Only participants enrolled in the study may receive study intervention and only authorized site staff may supply or administer study intervention. All study interventions must be stored in a secure, environmentally controlled, and monitored (manual or automated recording) area in accordance with the labeled storage conditions with access limited to the investigator and authorized site staff. At a minimum, daily minimum and maximum temperatures for all site storage locations must be documented and available upon request. Data for nonworking days must indicate the minimum and maximum temperatures since previously documented for all site storage locations upon return to business.
3. Any excursions from the study intervention label storage conditions should be reported to Pfizer upon discovery along with any actions taken. The site should actively pursue options for returning the study intervention to the storage conditions described in the labeling, as soon as possible. Once an excursion is identified, the study intervention must be quarantined and not used until Pfizer provides permission

to use the study intervention. Specific details regarding the definition of an excursion and information the site should report for each excursion will be provided to the site in the IP manual.

4. Any storage conditions stated in the SRSD will be superseded by the storage conditions stated on the label.
5. Study interventions should be stored in their original containers.
6. See the IP manual for storage conditions of the study intervention.
7. The head of the medical institution (where applicable) or study intervention administrator is responsible for study intervention accountability, reconciliation, and record maintenance (ie, receipt, reconciliation, and final disposition records), such as the IPAL or sponsor-approved equivalent. All study interventions will be accounted for using a study intervention accountability form/record.
8. Further guidance and information for the final disposition of unused study interventions are provided in the IP manual. All destruction must be adequately documented. If destruction is authorized to take place at the investigator site, the investigator must ensure that the materials are destroyed in compliance with applicable environmental regulations, institutional policy, and any special instructions provided by Pfizer.

Upon identification of a product complaint, notify the sponsor within 1 business day of discovery as described in the IP manual.

6.2.1. Preparation and Dispensing

Within this protocol, preparation refers to the investigator site activities performed to make the study intervention ready for administration or dispensing to the participant by qualified staff. Dispensing is defined as the provision of study intervention, concomitant treatments, and accompanying information by qualified staff member(s) to a healthcare provider, participant in accordance with this protocol. Local health authority regulations or investigator site guidelines may use alternative terms for these activities.

PF-06823859 and placebo will be prepared by qualified unblinded site personnel according to the IP manual. Blinded study intervention will be administered in a blinded fashion to the participant.

6.3. Measures to Minimize Bias: Randomization and Blinding

6.3.1. Allocation to Study Intervention

Participants will be randomly assigned to receive study intervention from a central randomization scheme. Investigators will remain blinded to each participant's assigned study intervention throughout the course of the study. In order to maintain this blind, an otherwise

uninvolved third party (for example, pharmacist) will be responsible for the preparation and dispensing of all study intervention according to the randomization schedule and assigned treatment for the individual participant.

6.3.2. Breaking the Blind

The method for breaking the blind in this study will be manual. A sealed envelope that contains the study intervention assignment(s) for each participant will be provided to the investigator. The sealed envelope will be retained by the investigator (or representative) in a secured area. In case of an emergency, the investigator has the sole responsibility for determining if unblinding of a participant's treatment assignment is warranted. Participant safety must always be the first consideration in making such a determination. If the investigator decides that unblinding is warranted, the investigator should make every effort to contact the sponsor prior to unblinding a participant's treatment assignment unless this could delay further management of the participant. If a participant's treatment assignment is unblinded, the sponsor must be notified within 24 hours after breaking the blind. When the blinding code is broken, the reason must be fully documented and entered on the CRF.

Once the study is complete, all envelopes (sealed and opened) must be inventoried and retained until authorization for destruction has been provided.

Blood specimens will be obtained from all participants for PK analysis to maintain the study blind at the investigator site. Only the investigator site staff and blinded study monitor, if assigned, will be blinded to study treatment. Other Pfizer personnel will be unblinded to participant treatments in order to permit real-time interpretation of the safety and PK data. The blinded study monitor, if assigned, will remain blinded to treatment until all monitoring for the study has been completed. Specimens from participants randomized to placebo will not be routinely analyzed. To minimize the potential for bias, treatment randomization information will be kept confidential by Pfizer unblinded personnel and will not be released to the blinded investigator or blinded investigator site personnel until the study database has been locked or the investigator requests unblinding for safety reasons.

